4. DATA ANALYSIS / SUBJECT SELECTION

Statistical and Analytical Plan

All participants who have consented to the study and completed at least one monitoring period of CGM use will be included in the data analysis set. Adverse events, vital signs, physical examination, and laboratory safety variables (Screening to Final Visit) will be reviewed and summarized on an ongoing basis during the study to evaluate safety. Safety data will be presented in tabular and/or graphical format and summarized descriptively, where appropriate.

Data will be stored using a secure, web-based application designed to support data capture for research studies (RedCap), providing: 1) an intuitive interface for validated data entry; 2) audit trails for tracking data manipulation and export procedures; 3) automated export procedures for seamless data downloads to common statistical packages; and 4) procedures for importing data from external sources. Data are stored and are backed up on a scheduled basis with data encryption for any regulated data types (private health data (PHI) which require backup media in an encrypted format. Data will be maintained in protected files at Joslin Diabetes Center. Only deidentified data will be transferred (via secure electronic file transfer) between collaborators.

CGM data, alarms, reported symptoms, need for assistance, hypoglycemia awareness scale, and timing of symptoms relative to sensor glucose levels will be recorded. We will also define CGM values, both during the day and night, using thresholds <55 (severe hypoglycemia)[32], 55-70 (moderate hypoglycemia), 70-180 (euglycemia), and >180 mg/dl (hyperglycemia).

CGM data will be analyzed in several ways: (1) minutes per day <70 mg/dl (primary analysis), (2) minutes per day <55 mg/dl, (3) number of episodes requiring assistance, (4) episodes of severe hypoglycemia (<55 mg/dl), (5) episodes of moderate hypoglycemia (55-70 mg/dl), and episodes of hyperglycemia (>180 mg/dl). In secondary analysis, data from days and nights (11 PM – 6 AM) will be analyzed separately. Activity measures, including total step number as well as duration of activity as defined by heart rate increment, will be analyzed to determine relationship to changes in sensor

Approved by
JDC/CHS 

glucose levels (Fitabase). For all data, paired analysis will be used to compare responses per participant for masked vs. unmasked periods.

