Analyses will utilize either parametric (paired t tests) or non-parametric statistical tests (Wilcoxon signed-rank test), depending on data distribution for continuous variables, and chi square for categorical variables.

Sample Size and Justification

Approximately 40 subjects may be screened for this study, assuming approximately 30% will not meet inclusion criteria. To allow for potential drop-outs (assuming 20%), 28 subjects will be enrolled with goal for 20 subjects to complete all study visits.

Prior data from our group in patients with symptomatic post-bypass hypoglycemia (n=10, unselected for severity) demonstrate mean \pm standard error of 63 ± 23 minutes/day for sensor glucose <70 [4]. This was a small cohort, (n=10), was unselected for severity, and utilized an early Medtronic diagnostic CGM system. The cohort proposed in this study is expected to have longer duration of hypoglycemia daily. However, we have used these data to estimate power for the current study. We estimate power of 98% to detect a 50% reduction (32 minutes) in time <70 with alpha 0.05 (2-sided) for paired comparison of masked and unmasked monitoring periods with a sample size of 20. As noted above, we expect power will be higher due to increased severity in this sample cohort; even with the conservative calculations, we should have adequate power (0.8) to detect differences between masked and unmasked periods as low as 23 minutes per 24 hours.

Data will be analyzed after 10 individuals have completed the paired analysis of response to masked vs. unmasked CGM analysis. At that time, power will be reassessed, and sample size will be adjusted if needed.

Local Interim Data Analysis/Data Monitoring Plan

Data will be stored using a secure, web-based application designed to support data capture for research studies (such as RedCap), providing: 1) an intuitive interface for validated data entry; 2) audit trails for tracking data manipulation and export procedures; 3) automated export procedures for seamless data downloads to common statistical packages; and 4) procedures for importing data from external sources. Data are stored and are backed up on a scheduled basis with data encryption for any regulated data types (private health data (PHI) which require backup media in an encrypted format.

Data will be maintained in protected files at Joslin Diabetes Center. Only deidentified data will be transferred (via secure electronic file transfer) between collaborators.

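### The 98% and 80% power figures for 20 completers rest on an SD of paired differences that the cited pilot data do not supply, so calling them conservative is unsupported

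*Combined protocol and SAP*

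**What the plan says.** All of this is in section 4 (Data Analysis / Subject Selection).

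- **Endpoint and comparison.** The primary measure is "minutes per day <70 mg/dl (primary analysis"), and "paired analysis will be used to compare responses per participant for masked vs. unmasked periods". The test is to be a paired t or a Wilcoxon signed-rank test, depending on the distribution.
- **Pilot data** (Sample Size and Justification). Ten patients, reported as a mean with "standard error of 63 ± 23 minutes/day for sensor glucose <70". The plan discloses that this cohort was small, "was unselected for severity, and utilized an early Medtronic diagnostic CGM system".
- **Use of the pilot.** "However, we have used these data to estimate power for the current study".
- **Power claims at 20 completers.** "We estimate power of 98% to detect a 50% reduction (32 minutes) in time <70 with alpha 0.05 (2-sided) for paired comparison"; and, on what the plan calls conservative calculations, "we should have adequate power (0.8) to detect differences between masked and unmasked periods as low as 23 minutes per 24 hours".
- **Direction of error.** "we expect power will be higher due to increased severity in this sample cohort".
- **Reassessment.** After 10 participants have paired data, power is to be reassessed and the sample size adjusted if needed.

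The document gives no SD of paired differences, no masked/unmasked correlation and no repeat-period pilot data. It does not say which test or formula produced the power figures.

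**The concern.** The power of a paired comparison depends on how much the change varies from one participant to another. A single-period standard error measures something else, the spread between participants at one time. The step from one to the other needs a correlation between periods and an SD for the unmasked period, and the plan gives neither.

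These two power figures are the only quantitative justification for 20 completers. If they depend on a favourable input that is not disclosed, a reader cannot judge whether 20 is enough. The words conservative and higher would then give reassurance that the cited data do not provide.

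**Working it through.** **Inputs from the plan:** n = 20 pairs; two-sided alpha 0.05; pilot mean 63, SE 23, n = 10; targets of 98% power at 32 min (half of 63 is 31.5) and 80% at 23 min.

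**1. Pilot SD.** SD = SE × √n = 23 × √10 = 72.7 min/day, between participants, one period.

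**2. SD of differences (s) that reproduces the plan's figures.**

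- Normal approximation: s = δ√n / (z₀.₉₇₅ + z_power).
  - 98% at 32 min: 32 × 4.472 / (1.960 + 2.054) = 35.7.
  - 80% at 23 min: 23 × 4.472 / (1.960 + 0.842) = 36.7.
- Paired t (noncentral t, 19 df, noncentrality δ√20/s), solved for s: 33.8 and 34.8.

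Within either method the two values differ by about 1 min, so the stated figures agree with each other. One unstated SD of about 34-37 probably lies behind both.

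**3. What that SD implies.**

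- Equal SDs in both periods: r = 1 − s²/(2 × 72.7²), which gives 0.89 and 0.89 (t), and 0.88 and 0.87 (normal).
- Unmasked SD halved along with the mean: s = 72.7 × √(1 + 0.25 − r). The smallest possible value, at r = 1, is 72.7/2 = 36.4, meaning every participant falls by exactly half. Normal approximation then gives 97.6% power at 32 min and an 80%-detectable difference of 22.8 min. Paired t gives 96.2% and 24.0 min.

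**4. Sensitivity, paired t, n = 20.** The SDs of differences are illustrative assumptions. The correlation column assumes equal SDs of 72.7.

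| SD of differences | Equal-SD correlation | Power for 32 min | Power for 23 min | 80%-detectable difference |
|---|---|---|---|---|
| 73 | 0.50 | 46% | 27% | 48 min |
| 56 | 0.70 | 68% | 41% | 37 min |
| 46 | 0.80 | 84% | 56% | 30 min |
| 36 | 0.88 | 96% | 77% | 24 min |

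**5. Wilcoxon, simulated.** Assumptions: lognormal minutes/day, masked mean 63 and SD 72.7, unmasked mean and SD reduced by the same factor, correlation 0.7, n = 20, exact critical value 52. Power is about 99% for a halving and about 80% for 23 min, with SDs of differences of about 54 and 52. A gamma distribution needs more correlation: for a halving, 67% at r = 0.54, 91% at 0.76 and 99% at 0.88.

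**6. Severity.** Start from SD of differences 46 and a 32 min effect (84%). Raise the mean 1.5-fold, so that a 50% cut is 48 min. Paired-t power is 99% if the SD stays at 46, 84% if it rises in proportion to 69, and 60% if it doubles to 92.

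**The case against.** The strongest reply is that the figures can be recovered from the plan's own numbers. Apply the stated 50% reduction uniformly, use the normal approximation, and 97.6% and 22.8 min round to 98% and 23 min. This stands as a possible route. It rules out any claim of an arithmetic slip, but uniform halving is a strong assumption that the plan does not state.

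A second reply is that the plan allows a Wilcoxon test. Minutes per day cannot be negative, and a mean of 63 with an SD near 73 points to skewed data, so normal-theory figures may understate power. This also stands, and it means an SD of differences of 34-37 is not a necessary condition. The plan, however, names neither the test nor a distribution for its power figures.

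Third, conservative may refer only to a pilot cohort unselected for severity. Even so, the severity argument works only if the SD of differences rises less than in proportion to the mean. That may be true, but nothing in the plan supports it.

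Three stronger readings are tempting and should not be drawn:

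- *True power is 46%.* That row needs a correlation of about 0.5 with equal SDs. The documents support that value no better than a higher one.
- *The standard error was mistaken for an SD.* Using 23 as the per-period SD with no correlation (s = 23 × √2 = 32.5) gives 98.6% and 85.1% by paired t. Using 23 as the SD of differences gives about 100% and 99%. Neither matches the stated 80%.
- *The trial is shown to be underpowered.* Nothing here shows that. The plan also discloses the weakness of the pilot and schedules a reassessment after 10 pairs, which can use real paired differences.

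**Conclusion.** The concern holds as a matter of support: the stated powers do not follow from the pilot summary alone, and the input that produces them is neither given nor sourced. Under the paired t or normal formula that input is about 34-37 min, half the pilot SD or slightly less. This is close to a best case: if the unmasked SD halves with the mean, 36.4 is the lowest value possible. Over the illustrative range of 36 to 73, power for 32 min runs from 96% down to 46%, and the 80%-detectable difference from 24 to 48 min.

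These results assume the pilot SD carries over to this cohort. That SD comes from 10 patients and is imprecise. The figures are not shown to be impossible, since a signed-rank test on lognormal data reaches them at a correlation near 0.7. The primary endpoint and the planned tests are unaffected. The point should be fixed because the justification for 20 completers rests on these numbers and on the unsupported description of them as conservative.

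**What to change.** Rewrite the power paragraph under Sample Size and Justification:

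1. Give the pilot SD (about 73 min/day) and say that it describes a single period. A normal-theory interval for it need not be printed.
2. State the assumed SD of paired differences, or the correlation and the unmasked SD, with its basis. Name the test and the distribution used for the calculation.
3. Replace the single 98% and 23 min with a range labelled illustrative, such as the table in the working, together with a Wilcoxon version under a stated skewed distribution. Keep 98% and 23 min only if the test and paired-difference assumptions that produce them are stated and justified.
4. Remove the description of the calculation as conservative. Remove the expectation of higher power, or make it conditional on the SD of differences rising less than in proportion to the mean.
5. Say that the reassessment after 10 pairs will use the observed paired differences.

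The cost is one paragraph and probably a less favourable stated power. The rewrite itself adds no enrolment; any change in sample size would come through the reassessment already planned.
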